7.3.2 RANDOMIZATION

Day 1

This visit must occur within 10 to 22 days of Screening Visit 1. Subjects with a period of more than 12 days between Screening Visit 2 and Day 1 are to be screen failed due to the lengthened time between baseline questionnaires and study medication injection.

The following procedures and assessments will be performed at Day 1 prior to randomization:

- Review and/or documentation of current and past medical history, documentation of current medications, and review of prior medication excluded by the protocol
- Physical examination, including knee examination of both knees
- Vital signs measurements (pulse, blood pressure, respiration rate, and temperature)
- Review of pain NRS electronic diary compliance from Screening Visit 2 to Day 1
- Electronic questionnaire review (WOMAC)

Results from these evaluations will be compared with inclusion/exclusion criteria to determine subject eligibility.

Physician Global Assessment will also be performed prior to randomization; however, results from this assessment do not determine eligibility.

The following randomization cohorts will be available until the associated subject counts are reached:

- Unilateral OA with $WPI \leq 4$ and $SSQ2 \leq 2$ – 240 subjects
- Bilateral OA with $WPI \leq 4$ and $SSQ2 \leq 2$ – 240 subjects
- Unilateral OA with $WPI > 4$ and/or $SSQ2 > 2$ – 60 subjects
- Bilateral OA with $WPI > 4$ and/or $SSQ2 > 2$ – 60 subjects

In order for a subject to be eligible for randomization, WPI&SS scores and subject bilateral/unilateral OA of the knee status from Screening Visit 1 must be entered into EDC prior to the study reaching the enrollment caps described above.

The following procedures and assessments will be performed at Day 1 following randomization:

- Intra-articular study medication injection (or placebo)
- Collection of TEAE and concomitant procedures/medication data
- Evaluation of success of blinding

Note: After the Day 1 site visit, subjects will complete monthly (every 4 weeks) WOMAC, KOOS, and Patient Global Assessment, weekly (every 7 days) KOOS-PS, and daily pain NRS and NSAIDs electronic diary completion in the evening (between 5:00 pm and 11:59 pm) remotely on their electronic devices. Refer to [Section 7.3.7](#) for a schedule of electronic diary and

questionnaire completion.

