5.1 PARTICIPANT INCLUSION CRITERIA

In order to be eligible for the study, subjects must fulfill all of the following criteria:

1. Males and females between 40 and 80 years of age, inclusive, in general good health
2. Ambulatory
3. Diagnosis of femorotibial OA in the target knee by standard American College of Rheumatology (ACR) criteria at Screening Visit 1 (clinical AND radiographic criteria); OA of the knee is not to be secondary to any rheumatologic conditions (e.g., rheumatoid arthritis)
4. Pain compatible with OA of the knee(s) for at least 26 weeks prior to Screening Visit 1
5. Primary source of pain throughout the body is due to OA in the target knee
6. Daily OA knee pain diary average NRS intensity score ≥ 4 and ≤ 8 in the target knee on the 11-point (0-10) NRS scale for the 7 days immediately preceding Day 1
7. Pain NRS scores recorded for the target knee on at least 4 out of the 7 days immediately preceding Day 1
8. Daily OA knee pain diary average NRS intensity score < 4 in the non-target knee on the 11-point (0-10) NRS scale for the 7 days immediately preceding Day 1
9. Pain NRS scores recorded for the non-target knee on at least 4 out of the 7 days immediately preceding Day 1
10. Total WOMAC score of 96-192 (out of 240) for the target knee at baseline regardless of if the subject is on symptomatic oral treatment (baseline questionnaire completed during the screening period prior to randomization)
11. Willingness to use an electronic diary on a daily basis in the evening for the screening period and 24-week study duration
12. Negative drug test for opioids and drugs of abuse, except alcohol and marijuana, at Screening Visit 1
13. Subjects with depression or anxiety must be clinically stable for 12 weeks prior to Screening Visit 1 and, if on treatment for depression or anxiety, be on 12 weeks of stable therapy
14. Full understanding of the requirements of the study and willingness to comply with all study visits and assessments
15. Subjects must have read and understood the informed consent form, and must have signed it prior to any study-related procedure being performed
16. Subject's Screening Visit 1 visit must occur while enrollment into the randomization cohort for which they are eligible is open

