10.5 SAMPLE SIZE

A sample size of approximately 630 subjects will be randomized at a ratio of 1:1:1:1:1:1 (0.03 mg active per 2 mL injection : 0.07 mg active per 2 mL injection : 0.15 mg active per 2 mL injection : 0.23 mg active per 2 mL injection : 0.0 mL vehicle : 2.0 mL vehicle). The sample size for this study was based upon accepted dose finding statistical practice (Ting et al. 2017).

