10.6 MEASURES TO MINIMIZE BIAS

10.6.1 BLINDING PROCEDURES

This is a double-blind study. Study medication will be provided to the investigational center. The investigational center must identify unblinded personnel who will be responsible for preparing the appropriate dilution of the study medication and who are able to perform the injection of study medication and/or vehicle. Study personnel administering or preparing study medication and reference therapy must minimize any contact with the subject following the injection and may not perform any study assessments throughout the duration of the study. Each site will be required to document a blinding plan that identifies the blinded and unblinded personnel at the investigational center and describes how the study blind will be maintained.

Subjects will be assigned a subject number at their Screening Visit 1. On Day 1, eligible subjects will be randomized via the Medidata database. Upon randomization of a subject, a Treatment Arm Notification email will be sent from [contact] to the unblinded investigational staff member designated in the Site-Specific Blinding Plan. Subjects will be randomized 1:1:1:1:1:1 (0.03 mg active per 2 mL injection : 0.07 mg active per 2 mL injection : 0.15 mg active per 2 mL injection : 0.23 mg active per 2 mL injection : 0.0 mL vehicle : 2.0 mL vehicle) to each treatment group using a permuted block design stratified by presence of bilateral knee OA (50% bilateral, 50% unilateral) and WPI&SS (80% $WPI \leq 4$ and $SSQ2 \leq 2$, 20% $WPI > 4$ and/or $SSQ2 > 2$). Specific information regarding the use of Medidata Balance to store and implement the permuted block design will be detailed within the SAP.

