3.1. Sample Size

A sample size of approximately 630 subjects was randomized at a ratio of 1:1:1:1:1 (0.03 mg active per 2 mL injection : 0.07 mg active per 2 mL injection : 0.15 mg active per 2 mL injection : 0.23 mg active per 2 mL injection : 0.0 mL vehicle : 2.0 mL vehicle). The sample size for this study was based upon accepted dose-finding statistical practice ([Ting et al. 2017](#)).

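### Do cohort counts that add up to 600 contradict a planned sample size of about 630?

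*Protocol*

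**What the plan says.** Protocol Section 10.5 gives the planned size: "A sample size of approximately 630 subjects will be randomized at a ratio of 1:1:1:1:1:1". The Protocol Summary and Section 4.1 give the same total. Section 10.6.1 repeats the ratio: "Subjects will be randomized 1:1:1:1:1:1". It sets the strata at half unilateral and half bilateral knee OA, and at 80% without and 20% with widespread pain or symptoms (WPI above 4 and/or SSQ2 above 2).

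Section 7.3.2 contains the closing rule: "The following randomization cohorts will be available until the associated subject counts are reached". The counts are 240 unilateral and 240 bilateral subjects without widespread pain, and 60 and 60 with it. The same section calls these numbers caps.

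Two provisions say what a full cohort prevents. Inclusion criterion 16 in Section 5.1 reads: "Subject's Screening Visit 1 visit must occur while enrollment into the randomization cohort for which they are eligible is open". Sections 7.3.1 and 7.3.2 add that the laterality status and pain scores must be in the EDC system before the caps are reached. Neither provision requires randomisation itself to come before the cap.

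SAP Section 3.1, in the past tense, says: "A sample size of approximately 630 subjects was randomized at a ratio of 1:1:1:1:1". It then lists six arms.

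**The concern.** The two totals stand in the same protocol and are never reconciled. The caps are exactly the 50/50 by 80/20 split of 600, so they look as if they were built for a trial of 600 and left alone while the total was given as 630.

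The total matters more than usual here because it is the only planning figure. There is no effect size, standard deviation, power or precision target behind it; Section 10.5 refers only to accepted dose-finding practice. Two of the three populations for the primary analyses (Section 10.4.2) are subsets defined by the stratification factors, so their sizes follow directly from the caps. If the caps were a hard stop, every arm and both unilateral populations would be about 5% smaller than a reader scaling from 630 would expect. An over-run concentrated in one cohort would shift the phenotype mix behind the all-subjects estimate.

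**Working it through.** **Inputs.** Caps 240, 240, 60, 60 (Protocol 7.3.2). Total about 630, six arms, 1:1 (Protocol 10.5, 10.6.1). Strata 50/50 and 80/20 (Protocol 10.6.1, SAP 3.2). Block size 6 (SAP 3.2). Day 1 falls 10 to 22 days after Screening Visit 1 (Protocol 7.3.2). Study duration about 11 months, participant duration up to about 27 weeks (Protocol Summary).

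**1. The totals.** 630 cannot be rebuilt from a power calculation, because none is given. The caps sum to 240 + 240 + 60 + 60 = 600. The gap is 30, which is 30/630 = 4.8% of the stated size or 30/600 = 5% above the caps. The cap shares are 40%, 40%, 10% and 10%, exactly the stated split.

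**2. What the caps stop.** Under criterion 16 and the EDC rule, a subject screened and entered before closure can be randomised after it. Appendix 3 (Amendment 01) gives that as the reason for tying criterion 16 to Screening Visit 1. The final total is therefore about 600 plus the eligible subjects still in screening when each cohort fills.

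**3. Is an over-run of 30 plausible?** An illustration, assuming uniform accrual over the planned period:

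- 11 months is about 335 days; less 27 × 7 = 189 days, about 146 days remain for entry.
- 600/146 = 4.1 randomisations per day.
- Subjects in screening who will go on to be randomised: 4.1 × 10 = 41 to 4.1 × 22 = 90.

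Late data entry, or sites stopping screening ahead of closure, would reduce this. An over-run of 30 is within reach, though this does not prove that it was the intent.

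**4. The worst case: no over-run at all.**

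| Population | Per arm from caps | Per arm scaled from 630 |
|---|---|---|
| All subjects | 600/6 = 100 | 630/6 = 105 |
| Unilateral | 300/6 = 50 | 315/6 = 52.5 |
| Unilateral, no widespread pain | 240/6 = 40 | 252/6 = 42 |

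The right-hand column is derived; the documents state none of those figures as a target. In each row the standard error grows by √(630/600) = 1.025, or 2.5%.

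For one pairwise comparison at two-sided 5%, power = Φ(d√(n/2) − 1.96). At an assumed standardised effect d = 0.4 in all subjects:

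- n = 105: Φ(2.898 − 1.96) = 82.6%
- n = 100: Φ(2.828 − 1.96) = 80.7%

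Over assumed effects of 0.2 to 0.6 the loss is 0.3 to 2.1 points in all subjects and 0.5 to 2.1 points in the two unilateral populations.

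**5. The phenotype mix.** Suppose all 30 extra subjects fell in one cohort. The unilateral share would lie between 300/630 = 47.6% and 330/630 = 52.4%. The widespread-pain share would lie between 120/630 = 19.0% and 150/630 = 23.8%. If the treatment effect differed by δ between unilateral and bilateral disease, the all-subjects estimate would move by about 0.024δ; for the pain factor, by at most 0.038δ.

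**6. Balance between arms.** With blocks of 6 used in sequence, each stratum has at most one unfinished block. Arm counts then differ by at most 1 within a stratum and at most 4 over the four strata, whatever the total.

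**7. Would scaling the caps be better?** The split of 630 is 252/252/63/63. Since 63 is not a multiple of 6, two strata would close on a part-used block. The present 240 and 60 are both multiples of 6.

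**The case for a change.** The strongest case for acting is that the over-run is an inference. No passage says that 630 includes one, how large it may be, or how it is spread over cohorts. The two gates also differ: criterion 16 looks at the visit date, while Sections 7.3.1 and 7.3.2 look at data entry. A subject seen before closure but entered afterwards meets the first and fails the second, so the size of the over-run depends on how promptly sites enter data. The past tense in SAP Section 3.1 is only moderate support for 630, since it repeats the planned figure with the word approximately.

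All of that is fair as a comment on drafting, and one sentence would have spared the reader the question. It does not show a defect. The two gates do not conflict: a subject must pass both, and the EDC rule is simply the tighter. Nor does the silence leave the reader without actual numbers, because SAP Section 10.1 reports disposition by treatment group, site and randomisation cohort. Any over-run, and where it fell, will be visible. The ANCOVA as described adjusts only for the baseline value, so the all-subjects estimate does carry whatever mix results. By step 5 that is a small change of weighting, and by step 6 it does not favour any arm.

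**Conclusion.** The sum is right and the two totals are not reconciled, but the plan does not contradict itself. The counts of 240, 240, 60 and 60 are best read as thresholds for closing screening, which makes 600 roughly a floor and about 630 a reasonable expectation. This reading rests on criterion 16 and the EDC rule. That 30 is the expected over-run is an assumption.

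If the assumption fails completely, the cost is 2.5% on standard errors and about 2 points of pairwise power at most over the assumed effects. The documents make no power claim that this would undermine, and Protocol Section 10.2 states that no formal hypotheses are tested. The absence of a sample-size rationale is a separate matter and adds no weight here.

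The SAP describes randomisation as already done, so rewording the caps would alter neither the subjects enrolled nor any analysis. The missing term in its ratio is a clerical slip, plain from the six arms listed beside it and the six-term ratio in Protocol Sections 10.5 and 10.6.1. No change to the plan is needed.

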7.3.3 FOLLOW-UP

Week 4 and Week 12

The Week 4 and Week 12 visits should occur on Day 29 (with a window of + 3 days) and Day 85 (with a window of + 3 days), respectively.

The following procedures and assessments will be performed at each of these visits:

- Collection of TEAE and concomitant procedures/medication data
- Physical examination, including knee examination of both knees
- Vital signs measurements (pulse, blood pressure, respiration rate, and temperature)
- Venipuncture and collection of samples for clinical laboratory tests
- Physician Global Assessment

7.3.4 FINAL STUDY VISIT

Week 24 End of Study (EOS)

This final study visit should occur on Day 169 with a window of + 7 days.

The following procedures and assessments will be performed at Week 24 (EOS):

- Collection of TEAE and concomitant procedures/therapies/medication data
- Review of medical history
- Vital signs measurements (pulse, blood pressure, respiration rate, and temperature)
- Physical examination, including knee examination of both knees
- Weight measurement
- Venipuncture and collection of samples for clinical laboratory tests
- Radiograph – bilateral in weight-bearing fixed flexion position, posterior-anterior (PA) view X-ray
- Physician Global Assessment
- Evaluation of success of blinding
- Return of electronic device

7.3.5 EARLY TERMINATION VISIT

If possible, the following procedures and assessments should be performed within 14 days of subject premature withdrawal or termination:

- Collection of TEAE and concomitant procedures/therapies/medication data
- Review of medical history
- Vital signs measurements (pulse, blood pressure, respiration rate, and temperature)

- Physical examination, including knee examination of both knees
- Weight measurement
- Venipuncture and collection of samples for clinical laboratory tests
- Radiograph – bilateral in weight-bearing fixed flexion position, posterior-anterior (PA) view X-ray
- Physician Global Assessment
- Evaluation of success of blinding
- Return of electronic device

7.3.6 SCHEDULE OF EVENTS TABLE

Procedure	Screening Period ^a (Days -22 to -1)		Day 1 ^b	Week 4 (Day 29 +3 days)	Week 12 (Day 85 +3 days)	Week 24 (EOS) (Day 169 +7 days) / ET
	Screening Visit 1 (Days -22 to -10)	Screening Visit 2 (Days -12 to -7)				
Informed consent	X					
Inclusion & exclusion criteria	X		X			
Demographics	X					
Medical history	X		X			X ^c
Current and prior procedures/medications	X		X			
Serum pregnancy test	X					
Radiograph	X					X
Physical examination	X		X	X	X	X
Knee examination	X		X	X	X	X
Selection of target knee	X					
Height	X					
Weight	X					X
Vital signs	X		X	X	X	X
Clinical laboratory sampling	X			X	X	X
Urine drug test	X					
Electronic diary and questionnaire training ^d		X (eDiary device provision and training)				
WPI&SS ^e	X					
Pain NRS ^f			X (Review)			
WOMAC ^g			X (Review)			

Procedure	Screening Period ^a (Days -22 to -1)		Day 1 ^b	Week 4 (Day 29 +3 days)	Week 12 (Day 85 +3 days)	Week 24 (EOS) (Day 169 +7 days) / ET
	Screening Visit 1 (Days -22 to -10)	Screening Visit 2 (Days -12 to -7)				
Physician Global Assessment			X	X	X	X
Randomization			X			
Intra-articular injection			X			
TEAEs and concomitant procedures/medications			X	X	X	X
Evaluation of success of blinding			X			X
Return of electronic device						X

^a The screening period is a minimum of 10 days and a maximum of 22 days and includes Screening Visit 1 and Screening Visit 2; Screening Visit 2 should occur at least 3 days after Screening Visit 1, at between 7 to 12 days prior to Day 1, and after confirmation of eligible pregnancy test (if applicable), radiograph, clinical laboratory, and urine drug test report results.

^b At Day 1, all procedures should be performed prior to study medication injection except for collection of TEAE and concomitant procedures/medication data and the evaluation of success of blinding.

^c Review medical history to capture End Date(s), if applicable, of any ongoing medical history(ies) collected at screening.

^d Electronic diary devices will be provided to subjects at Screening Visit 2; subject electronic diary and questionnaire training will be conducted at Screening Visit 2.

^e WPI&SS will be administered on site at Screening Visit 1.

^f Electronic diary compliance for daily pain NRS over the screening period will be reviewed at Day 1 prior to randomization to determine subject eligibility.

^g WOMAC questionnaire will be reviewed at Day 1 prior to randomization to determine subject eligibility.

7.3.7 SCHEDULE OF ELECTRONIC DIARY AND QUESTIONNAIRE COMPLETION TABLE

	Monthly WOMAC, KOOS, and Patient Global Assessment	Weekly KOOS-PS	Daily pain NRS and NSAIDs electronic diary
Study Visit or Day	WOMAC, KOOS, and Patient Global Assessment will be completed by subjects on Screening Visit 2 + 5 days (or up until the day before the Day 1 visit) and monthly in the evening (between 5:00 pm and 11:59 pm) remotely on their electronic devices. Monthly questionnaires should be performed in the 2 days prior to each month (4 weeks) as outlined below.	KOOS-PS will be completed by subjects on Screening Visit 2 + 5 days (or up until the day before the Day 1 visit) and weekly in the evening (between 5:00 pm and 11:59 pm) remotely on their electronic devices. KOOS-PS should be performed in the 2 days prior to each week as outlined below.	Pain NRS and NSAIDs electronic diary should be completed daily starting after Screening Visit 2. Subjects will complete the diary in the evening (between 5:00 pm and 11:59 pm) remotely on their electronic devices. Diary completion should occur every day including on study visit days.
Screening Visit 1			
Screening Visit 2			
Screening Visit 2 + 5 days	Baseline monthly questionnaires (or up until the day before the Day 1 visit)	Baseline weekly questionnaire (or up until the day before the Day 1 visit)	Complete daily starting on the same day of Screening Visit 2 (after the visit); pain NRS assessments are to be completed for each knee.
Day 1			
Week 1 (Day 8)		Complete on Day 6 or 7	Starting on the same day of Day 1 (after the visit), pain NRS assessments are to be completed for the target knee only.
Week 2 (Day 15)		Complete on Day 13 or 14	
		Complete on Day 20 or 21	

	Monthly WOMAC, KOOS, and Patient Global Assessment	Weekly KOOS-PS	Daily pain NRS and NSAIDs electronic diary
Week 3 (Day 22)			Complete daily
	Complete on Day 27 or 28	Complete on Day 27 or 28	
Week 4 (Day 29)	Questionnaires should NOT be completed on same day as a study visit.		
		Complete on Day 34 or 35	
Week 5 (Day 36)			
		Complete on Day 41 or 42	
Week 6 (Day 43)			
		Complete on Day 48 or 49	
Week 7 (Day 50)			
	Complete on Day 55 or 56	Complete on Day 55 or 56	
Week 8 (Day 57)			
		Complete on Day 62 or 63	
Week 9 (Day 64)			
		Complete on Day 69 or 70	
Week 10 (Day 71)			
		Complete on Day 76 or 77	
Week 11 (Day 78)			
	Complete on Day 83 or 84	Complete on Day 83 or 84	
Week 12 (Day 85)	Questionnaires should NOT be completed on same day as a study visit.		
		Complete on Day 90 or 91	
Week 13 (Day 92)			
		Complete on Day 97 or 98	
Week 14 (Day 99)			
		Complete on Day 104 or 105	
Week 15 (Day 106)			
	Complete on Day 111 or 112	Complete on Day 111 or 112	
Week 16 (Day 113)			

	Monthly WOMAC, KOOS, and Patient Global Assessment	Weekly KOOS-PS	Daily pain NRS and NSAIDs electronic diary
		Complete on Day 118 or 119	Complete daily
Week 17 (Day 120)			
		Complete on Day 125 or 126	
Week 18 (Day 127)			
		Complete on Day 132 or 133	
Week 19 (Day 134)			
	Complete on Day 139 or 140	Complete on Day 139 or 140	
Week 20 (Day 141)			
		Complete on Day 146 or 147	
Week 21 (Day 148)			
		Complete on Day 153 or 154	
Week 22 (Day 155)			
		Complete on Day 160 or 161	
Week 23 (Day 162)			
	Complete on Day 167 or 168	Complete on Day 167 or 168	
Week 24 (Day 169)	Questionnaires should NOT be completed on same day as a study visit.		

7.4 JUSTIFICATION FOR SENSITIVE PROCEDURES

Not applicable for this study.

7.5 CONCOMITANT MEDICATIONS, TREATMENTS, AND PROCEDURES

Details regarding the name, indication, route of administration, dose, and frequency of all medications taken within 30 days prior to Screening Visit 1 through Week 24 (EOS)/ET will be recorded in the eCRF. “All medications” should include prescription, over the counter, supplements, as well as herbal or alternative medications. Subjects with a “yes” response for daily NSAID usage in their electronic diary should have a corresponding NSAID recorded in the eCRF.

Procedures or non-drug therapies that are ongoing, new, or modified at or after the Screening Visits must be recorded on the “Procedures and Non-Drug Therapies” page of the eCRF.

Any new or modified concomitant therapy must be considered to determine if it is related to a TEAE.

7.5.1 PRECAUTIONARY MEDICATIONS, TREATMENTS, AND PROCEDURES

Not applicable to this study.

7.6 PROHIBITED MEDICATIONS, TREATMENTS, AND PROCEDURES

Prohibited Concomitant Medications and Procedures:

- Any intra-articular injection, including glucocorticoids, hyaluronic acid derivatives, PRP, stem cell therapies, or other agents with therapeutic intent, into either knee is prohibited while the subject is on study; intra-articular injection of glucocorticoids, hyaluronic acid derivatives, PRP, stem cells, or other therapeutic agents into joints other than the knee is allowed.
- The following medications are prohibited while the subject is on study:
 - Opioids; short-term use of opioids as part of anesthesia or procedural sedation during the study period is permitted
 - Centrally acting analgesics (e.g., duloxetine) (refer to [Appendix 2](#))
 - Other anticonvulsants not listed in [Appendix 2](#) are also prohibited unless used for seizure or migraine prophylaxis
 - Systemic glucocorticoids greater than 10 mg of prednisone per day or the equivalent
 - Drugs of abuse except alcohol and marijuana
- Electrotherapy (refer to [Appendix 2](#)), acupuncture, and/or chiropractic treatments for knee OA are prohibited while the subject is on study.
- Any new formalized (i.e., prescribed by a medical professional) physical therapy exercise programs for knee OA are prohibited while the subject is on study; continuation of formalized physical therapy exercise programs that are already in

- progress at the time of screening are allowed.
- Planned or elective surgery, including arthroscopy, is prohibited while the subject is on the study. Non-surgical invasive procedures conducted for a diagnostic or therapeutic purpose that are scheduled during the study period are not prohibited. Examples include, but are not limited to: endoscopy, colonoscopy, bronchoscopy, cystoscopy, radiologic procedures such as coronary artery catheterization with or without intervention, and non-surgical cosmetic procedures such as Botox or other cosmetic injections.
 - Subjects are prohibited from participating in any other clinical research trial that includes the receipt of an investigational product or any experimental therapeutic procedure. Subjects are also prohibited from participating in any observational research trial related to osteoarthritis while on study.

The Investigator should notify the Samumed Medical Monitor immediately if any prohibited therapies are required to ensure subject safety.

